### **9.9 Research reimbursements**

Participants in the intervention arm will receive a financial reimbursement of R100 for participating in the research. This will be given after each interview. No incentives will be provided for intervention participation, but if an out-of-cluster site is needed for holding the workshops we will support travel costs to the venue. Refreshments for participants will be provided during the workshops.

Those participating in the control arm will receive R300 per interview. This amount has been chosen as it is a considerable incentive to participate, and we anticipate that it will be similar to the child support grant monthly amount in 2015 (which was R320 in 2014).

At follow up data collection points the amount of financial reimbursement and incentive for both arms will increase. For the intervention arm this will increase as such: baseline – R100; 12 months – R150; 24 months – R300. For the control arm this will increase as such: baseline – R300; 12 months – R450; 24 months – R600.

Retention in studies, particularly for control arms is highly challenging. Financial incentives have been used previously to improve retention. Research elsewhere has shown that financial incentives alone are not enough to prevent violent experiences or practices and so we anticipate that we can meaningfully incentivise the control arm without interfering with the study main outcome.

Facilitators and trial team members will receive no reimbursements for their time being interviewed, observed or during focus groups. If they need to travel for any specific research reason this will be reimbursed.

### **9.10 Working in informal settlements**

There are significant challenges to working and researching in informal settlements. To minimise these risks to our fieldwork team we build on the experience of delivering the pilot. At baseline Project Empower will have already secured access and provide us with detailed information about the local community, fieldwork will take place in a secure location and none of the fieldworkers will carry cash. All incentives will be transferred via cell phone through providing a reference number.

At 12 and 24 months Project Empower will once again re-establish entry to these communities to ensure security. In addition, they will hire community guides who will provide additional support as fieldworkers move around the community identifying participants. This has proved incredibly successful previously as community guides can provide local knowledge and are more likely to ensure safety.

Other strategies include fieldworkers only carrying cellphones for data collection – rather than laptops or tablets. Cell phones have a value of R1000 and are easy to hide, compared to lap tops or tablets. We also brief fieldworkers on fitting in e.g. by wearing appropriate clothes.

### **9.12 Additional Review bodies**

The University of KwaZulu Natal will also give ethics approval through its Human and Social Science Ethics Research Committee.

### **9.13 Similar studies**

We are not aware that the MRC Ethics Committee has previously been asked to approve a similar study.

## **10.0 Data handling and analysis**

### **10.1 Data management and data analysis from the main RCT**

All data will be co-owned by HEARD, the MRC and Project Empower.

Data will be uploaded by wireless from cell phones. The cell phone system is likely to be Mobenzi researcher. This is an online system that will automatically upload data if a connection is available. Given that this is in urban settings it is highly likely that a 3G connection will be continually available. If no signal is available, the cell phone stores the data until a connection is available. The cell phones have approximately 8 hours of battery time. Every evening they will be charged in readiness for the next day of work.

There is no direct data entry stage. The data is wireless uploaded onto a web-based data base that is preconfigured into the necessary dimensions. On a weekly basis the data base will be downloaded on to a staff computer in excel before being entered into STATA. Data will be managed, cleaned and stored by the Medical Research Council Gender and Health Research Unit. Data analysis for the main study outcomes will be conducted by the MRC Biostatistics Unit.

## 10.2 Data analysis

The main analysis will be by intention to treat but a *per protocol* analysis will also be conducted as a secondary analysis.

Any participant who responds affirmatively to any one of the five questions on physical intimate partner violence or three questions on sexual intimate partner violence in the past 12 months at the 24 month data collection points will be deemed to be an incident case of IPV victimisation (if female) or perpetration (if male).

IPV incidence will be compared between the study arms. The person years of exposure will be estimated as the time from the baseline to the first report of IPV (if this is reported during the study) or to the last interview, if they remain IPV free at the end of the study. Separate analyses will be done for males and females. The primary analysis will be carried out by fitting a Poisson regression model, which will terms for age of participant, cluster, baseline prevalence of IPV (for males or females) and treatment (arm). For each secondary outcome a Generalised Linear Mixed Models (GLMMs) will be fitted with similar terms as in the Poisson regression model for the main outcome. These will be fitted for time from baseline to interview (12 months and 24 months). Secondary analysis of the main outcome will also be done using a multi-level model for change. Generalised Linear Mixed model for binary outcome will be used.

Analyses for secondary outcomes will follow the same approach for variables where incidence can be measured. For outcomes using scales, the difference in the score/scale between baseline and 24 months measure will be assessed. For each of the scales a linear mixed model will be fitted with fixed terms for treatment arm. Separate models will be fitted for males and females. The scores will be directly calculated from the component items, while the scales will combine the items using weights determined by carrying out a principal component analysis on the items at baseline (separately for males and females), and using the loadings for the first principal component as the weight for each item. The baseline weights (separate for males and females) will be used to construct the scale at each time point. These analyses will firstly be carried out in the ITT population and then repeated for the per protocol population.

For any categorical variables where incidence cannot be calculated the following approach will be taken. First a cluster level analysis will be carried out with the response being the overall cluster proportion of participants who reported the practice, with this cluster level proportion being calculated separately for males and females. This response will be compared between clusters using an analysis of covariance model with terms for the overall cluster proportion of participants (males or females respectively) who reported the practice at baseline and treatment arm. The model will give the rate difference for the practice for participants in one arm versus those in the comparison, together with 95% confidence limits and a test of the null hypothesis that there is no difference between the two study arms in the proportion of participants who reported the practice. Separate estimates will be given for males and females as for the other responses. Further individual level analyses will be carried out by fitting Generalized Linear Mixed Models to the binary outcome variable. The model will have fixed terms for treatment arm and whether or not the participant reported the practice at baseline, with separate models fitted for males and females.

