### **7.10 Timing of data collection for main outcomes**

The baseline survey will be administered just after recruitment of participants and follow up surveys will be administered to the learners after 12 months and 24 months.

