3.5. Proposed Analyses

3.5.1. Primary analysis of primary outcomes

As described above, the primary analysis of the primary outcomes, will follow an intention-to-treat approach, with individuals analyzed according to the trial group to which their settlement was randomized. Since the clusters vary between 17-22 clusters between arms, we will conduct individual-level analysis, as it will be statistically more efficient and allow analysis of the effects of individual-level covariates. Mixed effects models will be used for quantitative outcomes i.e. continuous response variables, to take account of between-cluster variation. For binary outcomes, generalized estimating equations (GEE) will be used with an exchangeable correlation matrix and robust standard errors. GEE performs well for binary data more than the logistic regression random effects model and allow for clustering effects by assuming observations in the same cluster are correlated [Hayes & Moulton, 2017].

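### The protocol's primary IPV rate counts cases only at 24 months but stops person-time at a first report at any survey, and the SAP does not record that it replaces this analysis

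*Protocol*

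**What the plan says.** Protocol 10.2 gives two rules for the primary IPV rate.

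- **Cases.** A positive answer to any physical or sexual IPV item "in the past 12 months at the 24 month data collection points will be deemed to be an incident case of IPV victimisation" (perpetration for men).
- **Person-time.** "The person years of exposure will be estimated as the time from the baseline to the first report of IPV". Any report made in the course of follow-up has this effect; participants who never report IPV contribute time up to their final survey.

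Protocol 7.10 says that "follow up surveys will be administered to the learners after 12 months and 24 months", so a first report can come at either survey.

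The primary model in 10.2 is a Poisson regression with "terms for age of participant, cluster, baseline prevalence of IPV (for males or females) and treatment (arm"). The Executive summary lists the same terms. Neither place says whether cluster is fixed or random, and neither names a random effect, GEE or robust variance for this model. Randomisation is by cluster (7.6), with 17 clusters per arm (7.7). The outcome is physical and sexual IPV combined (7.8, main outcomes).

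The SAP of September 2018 takes another route. Section 3.5.1 says: "For binary outcomes, generalized estimating equations (GEE) will be used with an exchangeable correlation matrix and robust standard errors". Table 2 in 3.5.2 applies this to physical, sexual and severe IPV at 24 months, each as an odds ratio. The SAP contains neither person-time nor a Poisson model.

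**The concern.** An incidence rate needs one event definition: the event that ends a person's follow-up should be the event that makes that person a case. In 10.2 they differ whenever a participant reports IPV at 12 months. The resulting number estimates neither the rate of first report nor the 24-month prevalence, so its ratio between arms depends on 12-month reporting as well as on the 24-month effect.

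The second question is how cluster enters the model. In a cluster-randomised trial arm is constant within cluster, so an unspecified cluster term leaves it open whether the model can estimate the arm effect at all.

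At stake is the primary result for the protocol's main outcome, and whether a reader can trace the reported analysis from protocol to SAP.

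**Working it through.** The plan gives no worked value of this rate, so there is no figure to reproduce first.

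**1. What each response pattern contributes** (both surveys attended, at exactly 12 and 24 months)

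| 12 months | 24 months | Case under 10.2 | Person-years |
|---|---|---|---|
| yes | yes | yes | 1 |
| yes | no | no | 1 |
| no | yes | yes | 2 |
| no | no | no | 2 |

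With p12 and p24 the proportions reporting past-year IPV at each survey:

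rate = p24 / [p12 × 1 + (1 − p12) × 2] = p24 / (2 − p12)

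ratio of rates = (24-month prevalence ratio) × (2 − p12 in control) / (2 − p12 in intervention)

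The last factor is the contamination. It is below 1 when the intervention arm reports less IPV at 12 months, and above 1 when it reports more.

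**2. Effect at 12 months only.** Inputs: 41%, the pilot figure for women in 7.7.1; the 20–40% fall at 12 months is assumed. Set p24 = 0.41 in both arms.

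- 20% fall: p12 = 0.328 v 0.41, ratio = 1.59/1.672 = 0.951.
- 40% fall: p12 = 0.246 v 0.41, ratio = 1.59/1.754 = 0.906.
- The 24-month prevalence ratio is 1.00 in both.

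**3. Same effect at both surveys.** Inputs: 41 v 33, a row of the table in 7.7.1.

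- Control: 0.41/1.59 = 0.258 per person-year.
- Intervention: 0.33/1.67 = 0.198.
- Ratio 0.766, against a prevalence ratio of 0.33/0.41 = 0.805.

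**4. Comparison with a consistent rate.** Counting the first report at either survey gives (p12 + p24 − p11)/(2 − p12), where p11 is the proportion positive at both. The documents do not give p11. I assume a range from independence (p11 = p12 × p24) to p11 equal to 90% of the smaller of p12 and p24.

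| Scenario | As written | 24-month prevalence ratio | Consistent first-report ratio |
|---|---|---|---|
| 41 v 33 at both surveys | 0.766 | 0.805 | 0.805 (independence); 0.766 (50–90%) |
| 41 v 33 at 12 months only | 0.952 | 1.000 | 0.883–0.935 |
| 41 v 33 at 24 months only | 0.805 | 0.805 | 0.928–0.982 |

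The as-written ratio follows neither target consistently. Its level is also off: the control rate is 0.258, where a consistent first-report rate is 0.284 (90%) to 0.410 (independence).

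**5. How many participants are affected.** Control participants positive at 12 months only: 0.41 − 0.369 = 4% at the 90% end, and 0.41 × 0.59 = 24% under independence. Of 17 × 14 = 238 followed per arm and sex, that is about 10 to 58 people who lose follow-up and are never cases.

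**6. Cluster and arm in one model.** If cluster enters as indicators, the arm column is the sum of the 17 intervention-cluster columns: 34 indicators plus arm make 35 columns of rank 34. With intercept, age, individual baseline IPV and 33 indicators the rank is 36; adding arm gives 37 columns and the rank stays 36. Without cluster indicators (random effect or GEE), intercept, age, baseline IPV and arm have 4 columns and rank 4, and arm is estimable.

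**The case against.** Four points can be made for the plan.

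- **The case rule may be a slip.** The case definition speaks of data collection points in the plural, 7.7.1 relies on multiple assessments, and the censoring rule concerns those free of IPV throughout. All this fits an intended 12 and 24 months, which would remove the mismatch. That may be what was meant, but the text names only 24 months.
- **Cluster is never called fixed.** A reader might infer that the arm effect cannot be estimated. The documents do not support that as a flat statement. Where 10.2 means fixed terms it says so for other models, and its secondary-outcome mixed models are specified "with similar terms as in the Poisson regression model for the main outcome", which suggests that cluster could be random. The non-estimability is conditional; what stands is that the protocol does not say how cluster enters.
- **The SAP avoids both problems.** A reader might infer that two rival primary analyses are in force. That is too strong: the SAP is later, says it was finalised before database lock, calls the protocol's methods a short overview, and sets out its own primary analysis. But it contains no sentence replacing the Poisson analysis. Its severe IPV outcome pools all eight items but requires more than one occurrence, so a participant reporting one item once is a case under the protocol and not under that outcome.
- **The sizes depend on chosen inputs.** This stands. The documents give neither the timing of the effect nor the persistence of IPV. Part of the gap between 0.766 and 0.805 is also a difference of estimand, since a consistent first-report rate gives 0.766 too if persistence is the same in both arms.

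**Conclusion.** The point holds as a defect of wording in the protocol. The rate in 10.2 can be computed, but it is not a coherent incidence rate, because cases and person-time rest on different surveys. In the scenarios above the ratio is 0.95–0.91 where the 24-month effect is nil, and 0.766 where the prevalence ratio is 0.805. These figures assume full attendance and the stated reporting levels; they do not depend on persistence. The count of 10 to 58 participants per arm and sex does. The direction is not fixed: the rule favours the intervention only if that arm reports less IPV at 12 months.

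The arm effect is lost only if cluster is fitted as fixed indicators, which the protocol leaves open.

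Nothing here shows that an analysis run under the SAP would be distorted. What the SAP leaves unresolved is the protocol's own primary outcome: for physical and/or sexual IPV combined, the rule in 10.2 remains the only primary analysis stated in either document. It should be corrected.

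**What to change.** 1. Choose one definition for the combined outcome. Either analyse past-year physical and/or sexual IPV at 24 months as a binary outcome by GEE clustered on settlement, with baseline IPV and the SAP's covariates and no person-time; or, if an incidence rate is kept, count the first report at 12 or 24 months as the event and stop person-time at that same report.
2. State that cluster enters as a random effect or as the GEE grouping, not as fixed indicators, in 10.2 and in the Executive summary.
3. Add a dated statement to the SAP that its analysis replaces the Poisson person-time analysis, with the reason, and say how the protocol's combined IPV outcome is handled beside the separate physical, sexual and severe outcomes. Copying the SAP's method into the protocol would not be enough, because the SAP has no such outcome. A dated statement also keeps the change visible.

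The cost is wording in two documents. Both surveys and all items are already planned, so no new data are needed.

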### **Costing Analysis**

In order to estimate the total cost of the SS/CF intervention, the cost of both the retrospective and prospective components of the study outlined above will be analysed. This includes the direct and indirect costs from the perspective of the service providers and the participants. Research related costs will be excluded from the analysis.

In order to conduct the cost-effectiveness analysis, incremental cost-effectiveness will be calculated using primary and selected secondary outcomes of the SS/CF intervention. The primary outcome in the RCT is incidence in the past year of intimate partner violence (perpetration of physical and/or sexual IPV for men and victimisation for women), including change in controlling behaviour. Key secondary outcomes include gender attitudes; depression; problem drinking; sexual behaviour and mean earnings in last month. The time and motion data will be used together with the salary costs paid to the facilitators to identify the proportion of labour resources used and costs relating to core activities in the intervention, administrative activities and non-core activities.

Costs and outcomes are compared against the control group, who receive no intervention in the initial timeframe as set out in the RCT design. Cost-effectiveness will be assessed as the intervention cost per participant divided by the effectiveness of the intervention.

The cost data collected at different time points in the study will also be used to estimate the incremental efficiency gains as the facilitators become familiar with the intervention and the material they present. These data will be used to better understand resource use as the intervention rolls out and has implications for estimating the costs of scale-up.

We will use a standard annual discount rate of 3%, and run sensitivity analyses will be conducted using local discount rates, to check the robustness of results to these changes. Total costs will be reported in USD2017, using official exchange rates.

Concentrating on health outcomes exclusively would not do it justice and risk overlooking a large portion of its impact. Therefore impact on economic outcomes – including income, consumption, savings behaviour and preferences – will be assessed using the main analysis model, similarly to main outcomes, and analysed alongside willingness to pay. Estimation of willingness to pay will be based on participant responses to an open-ended contingent valuation question, and will include a multivariable regression analysis to identify key predictors of willingness to pay. This will not only provide a full representation of intervention impact, but also contextualise the willingness to pay results in relation to participants' socio-economic status and relevant changes as a consequence of the intervention.

## **11.0 Challenges**

We recognise that attendance at the intervention will be voluntary, the intervention is long and it is difficult to know exactly what the level of sustained participation will be. We will collect data on attendance so that we can use this information in the data analysis. In the pilot study we found approximately 60% of sessions were attended, and this showed promise of impact. We do not expect attendance to be lower than in the pilot. We also may encounter loss to follow up. We have inflated the necessary sample size to allow for a possible 40% loss to follow up without critical loss of power for the evaluation. Retention of participants is always a challenge in cohorts and plans for this are outlined below.

Informal settlements are tricky areas to work in because they can be dangerous for staff and also sometimes have quite complex local politics. Project Empower has been working in informal settlements in Durban since it was established 13 years ago and so we are confident that they have the necessary understanding of the issues in these areas to be able to undertake the mobilisation for the study and intervention safely.

### 11.0 Dissemination

The trial will be registered on [clinicaltrials.gov](http://clinicaltrials.gov) and information about the trial is available on the What Works to Prevent Violence website ([www.whatworks.co.za](http://www.whatworks.co.za)). The Stepping Stones manual is available through the MRC and the Creating Futures manual can be found on the HEARD website [67]. A paper on the methodology used and the main study findings from the RCT will be published in international peer reviewed journal articles.

The study team will form a local stakeholder group with representatives of participating communities through the structures consulted for consent, representatives from provincial Government in KwaZulu-Natal and NGOs working in similar areas who will be informed of the trial and emerging results. One meeting of this stakeholder group will be held annually for the four year duration of the project. During these meetings, participants will be informed about project progress, consulted on challenges, and informed of findings as these emerge.

Information about the trial will be disseminated to conferences and at meetings with stakeholders in the health, violence, gender and economic empowerment fields. Multiple strategies will be used to disseminate the important learnings that will be gained and to ensure the integration of these lessons into practices at a provincial level and beyond where possible. These strategies include: meetings and workshops, written outputs including fact sheets and brochures; global dissemination and discussions via SVRI platforms and activities. Initially, meetings will be held with decision-makers, both provincially and nationally to inform them of the project and to invite them to form part of the advisory bodies. Once these bodies have been established, regular meetings will be scheduled to keep members informed of project progress and to get input on various aspects of the project. Fact sheets, briefing papers and presentations will be developed to support project activities and assist with sharing project outcomes.

Finally, a national workshop with policy makers, community members, donors and other stakeholders will held to discuss the findings of the project and map a way forward for scaling up.

In addition, the team will create a short film (approximately 5 minutes) using interviews with facilitators and participants about their experiences of the intervention and the approach. The film will be ‘promotional’ and emphasise positive aspects of the intervention and approach. The film rationale is outlined in Appendix 33, with a short topic guide (Appendix 34) and informed consent for the participation in the film (Appendix 35).

